As per guidance from previous REC feedback, the below protocol has been briefly piloted and reviewed with two adolescent experts by experience (EBEs). In a series of meeting, we tested several components of the following design and we proceeded with minor amendments based on their feedback. Their feedback was used to inform the below study protocol.

Phase 0-A: Screening.

The participating NHS clinics will identify and screen potential participants using the inclusion criteria. The partnering NHS clinics will provide some information about the aims and objectives of the study to adolescents and their parents/ carers. The participants will be given a flyer containing the QR code link to Qualtrics, to begin the onboarding process.

Phase 0-B: Enrolment.

Using a QR link to a Qualtrics survey, participants (and their caregiver, if they are aged 12-16) will view the study information sheet and proceed to the consent/assent form, should they wish to participate. Consent will be obtained electronically via Qualtrics. Participants will receive a copy of the information sheet and completed consent/assent form via email. Upon gaining consent, we will contact participants to begin Phase 1.

Phase 1: pre-baseline.

Participants will spend a total of 1-2 weeks completing an online questionnaire (Process Based Assessment Tool; PBAT). Participants will receive completion prompts via the mPath app, on 3-4 days per week, and the questionnaire will take up to 3-4 minutes to complete. The PBAT questionnaire will collect data to track how adolescents cope with their headaches. This information will help the research team to develop the personalised plan for the psychological intervention in Phase 4 (described further on).

Phase 2: Personalisation and case conceptualization.

HeadFlex study

Project proposal, Royal Holloway University of London V3

Version and date: V3, September 2024

IRAS project number: 340890

PI: [name], C.Psychol (Clinical & Health) Royal Holloway, University of London

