
 - Adolescents aged 12-18. - Recurrent headaches occurring for 3 months or more, ideally (but not necessary)-diagnosed by a paediatric Neurologist (diagnosis of any idiopathic headache, using the International Classification of Headache Disorders criteria (ICHD-3 beta version). - The headache should be deemed to be resulting from a primary headache disorder as opposed to a secondary symptom of another health condition. - Currently not receiving psychological support elsewhere or have prior accengagement with psychological support for or due to headache for the past 6 months prior to screening. - Reporting PedMIDAS score of greater than 10 points (indicating at least minimal disability) - Adolescent and their caregiver fluent in speaking and writing in English - Frequent access to a smartphone and access to the internet whether public (e.g., library) or private (e.g., home, personal) 	
 - Presence, history or suspicion of secondary headache disorder- - PedMIDAS of greater than 140 points (indicating excessive disability and need for multisystemic therapies). - Adolescent and their carer not fluent in speaking and writing in English. - Diagnosis of pervasive developmental disorder or serious mental condition (eg, psychosis, active suicide thoughts) as determined by the referral (either the parent/carer or the medical professional) - Adolescents living in families in distress (e.g., a family member experiencing another illness, mental health problem or psychosocial issues) - Limited access to a smartphone device with consistent internet connection. - Receiving psychological support elsewhere or have a prior engagement with psychological support for headaches up to 6 months prior to screening.

Assessment procedures

Demographics and clinical characteristics

HeadFlex study

Project proposal, Royal Holloway University of London V3

Version and date: V3, September 2024

IRAS project number: 340890

PI: [name], C.Psychol (Clinical & Health) Royal Holloway, University of London

Demographic information will be collected using Qualtrics between Phase 1 and 2. This will include the adolescent's age, gender, cultural background, headache diagnosis, headache profile (e.g., frequency, intensity, severity), and medication use.

Measures

Primary outcome measures

The primary outcome measures will be a series of Visual Analogue Scale (0-100) items that measure the following:

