To address the second research question, we will examine change in personalised goal, headache activity (VAS items), and personalised processes of change (BPAT) across time. The longitudinal data will be plotted on a line graph to allow a visual analysis for patterns, trends and variability in the data (Dowdy et al., 2022). We will supplement the visual analyses with Tau-U statistical analyses to assess the proportion of overlap between phases.

We will additionally follow a tutorial by McDonald (2022) to conduct individual dynamic regression analyses using a time-lag model, using SPSS. We will develop models, based on periods of feedback provision (one per week- overall 5 tested models). For these analyses we will estimate the

autocorrelations with lag numbers representing previous data points (e.g., data from sessions 1-5 will be included). The lagged idiographic outcome variables (headache interference and activity) will be entered into the regression model along with predictor(s) (the BPAT items) to identify whether a significant relationship exists between the predictor and the outcome, while accounting for any autocorrelation.

Ethical considerations

This study will require ethical approval from the RHUL Ethics Committee and the NHS Research Ethics Committee. Research guidelines and principles of the BPS Code of Ethics and Conduct will be followed throughout the project. Several ethical issues arising from this research are detailed below:

Informed Consent

Informed consent will be sought from both the participant and their primary caregiver or parent. Consent will be obtained electronically and, and electronic signed copies of consent forms will be stored in a RHUL's databases, accessible only to the research team. Appropriate time will be given during enrolment to ensure that participants fully understand the purpose of the study and study requirements. Participants and their caregivers will be provided with an e-copy of the information sheet.

Participants and their caregivers will be made aware that their involvement with the study is fully voluntary and that they are able to withdraw from the study at any point without justification, which will not impact their reimbursement for participating. Participants will also be made aware that any data collected up until the point of withdrawal will be anonymised and retained for analysis, to protect the validity of the study.

HeadFlex study

Project proposal, Royal Holloway University of London V3

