Version and date: V3, September 2024

IRAS project number: 340890

PI: [name], C.Psychol (Clinical & Health) Royal Holloway, University of London

It is unlikely that issues with capacity to consent will occur during the study.

Confidentiality

All the outcome measures will be collected using the mPath app and Qualtrics and stored as per privacy regulations on a secure server at RHUL. Participants will each be assigned a numerical identifier only known to the researcher throughout the study, to maintain confidentiality. Data will be fully anonymised when collected and writing the results of the study. All identifying information will be stored on a password-protected file which is only accessible by the research team. Consent and assent forms will be kept as per institutional policies and then shredded.

The adolescent's GP will be aware of the adolescent's participation in the study. The participant and their caregiver will be informed that any adverse effects occurring during treatment (e.g. suicidal or self-harm risk) will be reported back to their GP, as well as their caregiver if the participant is under 16. In case of less than imminent risk, then the researcher will encourage the participant to contact their GP/mental health provider. The research team will also encourage the participants to talk to trusted family members or other community support resources, and pass the subject contact information for the suicide hotline or similar crisis management organizations. In case of high imminent risk, the researcher would act quickly to protect the safety of the research participant. This means that the researcher will stay with the participant until assistance arrives or the person is transported to clinical care. Procedures for calling 999 to contact the nearest NHS Emergency department will be sought. The researcher will then notify and seek for support from the main supervisors.

Adolescents will be provided with an optional debrief meeting towards the end of the study, should they wish to do this.

Risk

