It is possible that, while discussing difficulties in relation to headaches and taking part in psychological interventions, some themes of emotional distress may arise for the adolescents. For example, through completing EMA questionnaires adolescents may become increasingly aware of difficulties resulting from headaches. Contact details of ChildLine and Samaritans as sources of additional support will be provided on the participant information sheet and debrief sheet.

The research team (trainee and supervisor) will be available to contact via RHUL email throughout study participation, for any ad-hoc concerns that participants or caregivers wish to discuss.

As detailed in the above information regarding confidentiality, should participants indicate significant risk to themselves or others (e.g. self-harm, suicidal thoughts or intent), the participant's caregiver and health professional and/or GP will be made aware of this. This will be detailed in the consent form and study information sheet.

Data gathered from participants will be stored within mPath and Qualtrics. Participants will be assigned a numerical identifier only known to them and the researcher, to maintain confidentiality. Participants will be made aware of this when discussing consent to participate. The raw data will be stored by the researcher during the data analysis phase, and at this point will be deleted from the survey management tool.

In which aspects of the research process have you actively involved, or will you involve, patients, service users, or members of the public?

Please tick:

Design of the research *

Management of the research

Undertaking the research

Analysis of results

Dissemination of findings

None of the above

Details of EBE involvement

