School-hours will need to be considered during weekday data collection, due to the likelihood that mobile device use may not be permitted at school.

In order to meet with participants and their caregivers, all the meetings will occur online.

Participants will be reimbursed for taking part in the project. In line with RHUL guidance, up to £10 in vouchers will be reimbursed to participants upon completion of the study. Should a participant or their caregiver wish to withdraw prior to study completion, they will nevertheless receive the reimbursement for participation.

Two participants who will act as experts by experience in the study will instead receive £50 each as a compensation for their additional contribution.

Dissemination

Participants will be provided with an option to receive feedback on the results of the study upon completion, by selecting this option on the initial consent form. The findings from the study will be presented to trainee clinical psychologists at RHUL as part of final year research presentations.

We will aim to submit the paper to a peer-reviewed journal such as the Journal of Pediatric Psychology (APA) or Behavioural Research and Therapy (BRAT).

References

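### The protocol gives two different rules for telling caregivers about suicidal or self-harm risk at ages 16-18, and two different rules for caregiver consent at ages 17-18

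*Protocol*

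**What the plan says.** Eligibility in Table 1 is "Adolescents aged 12-18", so 16-, 17- and 18-year-olds can enter.

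**Telling the caregiver about risk.** Under Ethical considerations, the Confidentiality section says what participants and caregivers will be told in advance: adverse effects during treatment, with suicidal or self-harm risk as the examples, "will be reported back to their GP, as well as their caregiver if the participant is under 16". The Risk section returns to the subject, refers back to the confidentiality text, and says that where a participant indicates significant risk, "the participant's caregiver and health professional and/or GP will be made aware of this". It gives no age condition, and adds that the consent form and information sheet will set this out.

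**Caregiver consent.** In Phase 0-B (Enrolment), "participants (and their caregiver, if they are aged 12-16) will view the study information sheet" and then go on to consent or assent. The Informed Consent section reads: "Informed consent will be sought from both the participant and their primary caregiver or parent". It gives no age condition.

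**Imminent risk.** The Confidentiality section says that "the researcher will stay with the participant until assistance arrives or the person is transported to clinical care". The practical arrangements set out shortly before Dissemination say that "all the meetings will occur online".

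**The concern.** A protocol can set any defensible age at which caregivers are told of risk or asked for consent, but it has to set one for each purpose. Here the reader finds two for each, and the answer for an older adolescent depends on which page is open.

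The notification conflict matters more. Both statements describe what families will be told about the limits of confidentiality. If the consent form follows one section and the therapist follows the other, a 17-year-old could be given an assurance about the caregiver that is then not kept, or a caregiver could expect a call that does not come. The protocol expects that distress may surface during the sessions and the repeated questionnaires, so it foresees that the rule may be needed.

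The consent conflict affects every participant aged 17 or 18, whether or not risk arises. Staff would not know whether the enrolment of a participant of that age is complete without a caregiver's consent.

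**Working it through.** No arithmetic applies. The check is to read the four statements against each eligible age.

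| Age | Caregiver told of risk: Confidentiality | Caregiver told of risk: Risk | Caregiver in consent: Phase 0-B | Caregiver in consent: Informed Consent |
|---|---|---|---|---|
| 12-15 | Yes | Yes | Yes | Yes |
| 16 | Not provided for | Yes | Yes | Yes |
| 17-18 | Not provided for | Yes | Not provided for | Yes |

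1. *Notification.* The two sections agree for ages 12 to 15 and differ for ages 16 to 18. The Confidentiality wording makes the caregiver's inclusion conditional on being under 16, so from 16 the condition fails and only the GP remains. The Risk wording includes the caregiver at every age.

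2. *Is the trigger the same?* If the two sections dealt with different levels of risk, both could stand. They do not. Confidentiality covers any adverse effect during treatment, and its examples are suicidal and self-harm risk. Risk covers significant risk to self or others, with self-harm and suicidal thoughts or intent as examples. The second falls inside the first where the risk is to the participant, and it cites the first as its source.

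3. *Consent.* The two statements agree for ages 12 to 16, because the Phase 0-B range includes 16. They differ for ages 17 and 18.

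4. *Are the two conflicts one problem?* No. Consent to take part and disclosure of risk are different matters and may properly use different ages. The conflict lies within each pair, and the fact that 16 is treated differently in Confidentiality and in Phase 0-B is not an error in itself.

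5. *Imminent-risk step.* Read literally, "the researcher will stay with the participant until assistance arrives or the person is transported to clinical care" suggests a researcher in the same room, while intake, therapy and other meetings are online. It can also mean remaining on the call while the emergency services are contacted, which the same paragraph provides for. The protocol does not say which is meant.

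**The case against.** The strongest defence is that the Risk section is a summary. It points back to the confidentiality text, so it may simply have dropped the age qualifier, and a careful reader would restore it. It can be added that the Confidentiality sentence does not contain the word 'only', that the GP or another health professional is told under both sections, and that the emergency steps for imminent risk carry no age condition. The disagreement is therefore about one recipient of information, the caregiver. The consent form and information sheet are not available here and may state a single clear rule.

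Much of this is fair, and it limits the finding. A reader might infer that staff face opposite instructions in an emergency. The text does not go that far, since the emergency response itself is the same at every age. The defence does not remove the conflict, however. The Risk section says that its own version will be detailed in the participant documents, and that version has no age limit. Whether the omission was accidental cannot be told from the page.

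A reader might also infer that caregivers who must be told of risk will never have been enrolled. This could concern only ages 17 and 18, and it rests on the Phase 0-B parenthesis alone. Elsewhere caregivers are involved without an age limit: in the language criterion in Table 1, in Informed Consent, in the information given under Confidentiality, and in the online meetings. The consequence is possible but not shown.

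Finally, a reader might conclude that the imminent-risk step cannot be carried out in this study. The wording allows remaining on the call, so it is ambiguous and does not amount to a demonstrated contradiction. Nor does the protocol say that all contact is online: it says this of meetings, and clinic staff do the screening.

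**Conclusion.** The point holds as two separate contradictions in the current text. The rule for telling a caregiver about suicidal or self-harm risk differs between Confidentiality and Risk for participants aged 16 to 18. The rule for caregiver consent differs between Phase 0-B and Informed Consent for participants aged 17 and 18. The imminent-risk wording is a minor ambiguity beside these.

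The size cannot be put as a number of participants. It is tempting to count ages: 16 to 18 is 3 of the 7 eligible years, 3/7 = 43%, and 12 × 3/7 = 5.1, or about 5 of the 12 to be recruited. That figure should not be used. It assumes an even spread of ages, for which the protocol gives no support. It also counts everyone of those ages, although the notification conflict operates only when such a participant shows risk, and active suicidal thoughts as identified by the referrer are an exclusion criterion. It would not describe the consent conflict either, which covers two of the seven ages.

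The conclusion assumes that 12-16 includes 16-year-olds, and that the age condition in Confidentiality is meant to exclude caregivers from 16 upwards, which is its ordinary sense. It does not depend on what the consent form says. The conflicts have no bearing on the analysis or the estimates, but they touch confidentiality and the safety of young people, so they should be settled before recruitment.

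**What to change.** - Reconcile the Confidentiality and Risk sections so that a single rule states when a caregiver is told of suicidal or self-harm risk.
- Reconcile Phase 0-B with Informed Consent so that a single rule states for which ages caregiver consent is sought. The two rules need not share an age threshold.
- Carry both rules in identical terms into the consent form and the information sheet, and check any existing versions against them.
- Reconcile the imminent-risk step with the statement that meetings are online, so that its meaning is clear.

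Which rule applies in each case, and how the imminent-risk step should operate, is for the clinical lead and the ethics committee. The cost is a few sentences in the protocol and the participant documents, with whatever approval such a change needs. No data collection or analysis is affected.

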School-hours will need to be considered during weekday data collection, due to the likelihood that mobile device use may not be permitted at school.

In order to meet with participants and their caregivers, all the meetings will occur online.

Participants will be reimbursed for taking part in the project. In line with RHUL guidance, up to £10 in vouchers will be reimbursed to participants upon completion of the study. Should a participant or their caregiver wish to withdraw prior to study completion, they will nevertheless receive the reimbursement for participation.

Two participants who will act as experts by experience in the study will instead receive £50 each as a compensation for their additional contribution.

Dissemination

Participants will be provided with an option to receive feedback on the results of the study upon completion, by selecting this option on the initial consent form. The findings from the study will be presented to trainee clinical psychologists at RHUL as part of final year research presentations.

We will aim to submit the paper to a peer-reviewed journal such as the Journal of Pediatric Psychology (APA) or Behavioural Research and Therapy (BRAT).

References

